### 10.4.4 ANALYSIS OF THE EXPLORATORY ENDPOINT(S)

*DAOOH*: Will be compared using T test or Wilcoxon rank-sum test, as appropriate.

If the distribution of 30 or 90 days *DAOOH* is skewed, the T test may not perform satisfactorily. An alternative approach to evaluate the robustness of the analysis, is to treat *DAOOH* as an ordinal outcome and use the proportional odds (PO) regression model to compare the two arms. The PO model is a generalization of the Wilcoxon (Mann-Whitney) test to estimate the shift in the underlying distribution of *DAOOH* by the intervention. The PO regression allows for adjustment of baseline covariates to enhance power.

We will examine the distribution of B-lines measurements for the groups with and without events separately. Both absolute number and relative change will be evaluated. Receiver Operating Characteristic (ROC) curves will be plotted together with area under the curve (AUC) calculated to understand the prediction performance of the B-line measurements. Sensitivity, specificity, positive and negative predictive values will be computed at a number of thresholds of B-line measurements to understand the trade-off between false positive and false negative. Confidence intervals of statistical measures will be constructed using the bootstrap method. Although 15 B-lines have been previously identified as a valid threshold, an alternative number may be more useful in the ED setting.

For reproducibility analysis, generalized linear mixed-effects models will be fitted to estimate the inter- and intra-observer variability, where both patients and observers are treated as random effects.

We will compare parameters used to identify congestion. This will include a comparison between B-lines measurements and other markers, such as physical exam, NTproBNP, eGFR, and hemoglobin/hematocrit. Bootstrap method will be used for the comparison to account for correlations between the markers and the B-line measurements. We will consider two strategies to explore potential multivariate models:

1. *Logistic regression models*: We will consider three different models. First, we include all markers together with B-line measurements in the model (Model 1). Second, we will explore all main effects models that can be built using the B-line measurements along with the other markers and select the one with the best model fitting characteristic (e.g. Akaike Information Criterion or Bayesian Information Criterion) (Model 2). Third, we will explore all main effects models that can be built using only the other markers (Model 3). These models will allow us to create a discriminating score for the prediction of 30 or 90-day outcomes.

2. *Tree based nonparametric method:* We will employ the classification tree to build a nonparametric prediction model using B-lines measurements and the seven other markers. (Model 4). We will build a similar classification tree without the involvement of the B-lines measurements (Model 5).

Models 1-5 will be evaluated using data from the testing set in terms of prediction accuracy. In particular, Models 2 and 3, 4 and 5 will be compared (if there is a difference between models 2 and 3, and between 4 and 5) to understand the net reclassification rate. Statistical inference of the comparison will be performed using the bootstrap method.

---

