### **Lung Ultrasound**

For years, the lungs have been considered ‘off-limits’ to ultrasound: with aerated lungs, the ultrasound beam is reflected and scattered due to acoustic mismatch. However, in the setting of pulmonary congestion, extra vascular lung water (EVLW) can be directly visualized and quantitated. Lung ultrasound measurement of B-lines are an objective, semi-quantitative measure of extra vascular lung water (EVLW). B-lines are well-defined, vertical echogenic lines, originating from water-thickened interlobular septa. (Figure 1) They are a marker of congestion.

LUS improves diagnostic accuracy and is highly reproducible. Intra and inter-observer variability of B-line capture and summary have been reported as low as 5.1% and 7.4%, respectively. In a recent meta-analysis, LUS was the best test to affirm the diagnosis of AHF, more than natriuretic peptide (NP) (likelihood ratio positive for the diagnosis of AHF by LUS was 7.4 (95% CI 4.2-12.8) and LR negative 0.16, (95% CI 0.05-0.51)). This may reflect the additional value of LUS when patients have chronically elevated NP levels. Recent guideline and consensus statements also support the use of LUS for diagnosis.

Importantly, B-lines are a dynamic marker. In dialysis patients, B-lines decrease markedly pre/post dialysis. In AHF patients, B lines generally decrease throughout hospitalization. However, persistence of B-lines pre-discharge identifies patients at higher risk for worse outcomes. B-lines even outperformed BNP as a prognostic marker. Finally, serial measurement of B-lines are both easy to learn and perform. LUS is also low cost, and does not involve radiation. Computerized diagnostic aids have already been pilot tested with excellent results, demonstrating the ease of B-line scoring. Hand held machines perform as well as a standard ECHO platform or US machines. **The ease of LUS will facilitate its generalizability and dissemination.** Non-physicians may be future users of bedside LUS assessment, further supporting its generalizability.

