**Prior Studies**

*Sonographic evidence of pulmonary congestion is associated with worse outcomes.*

We performed a single center pilot study of 44 patients who presented to the ED with dyspnea, evidence of B lines by LUS, and were admitted for AHF. Patients underwent LUS imaging during the ED (T0), within 24 hours (T1) and at discharge (Td). Vital status was determined by phone follow up within 90 days. Using a pre-specified cut-off of 15 B-lines as a marker of persistent pulmonary congestion, 50% of patients had evidence of EVLW at Td. The 28 sector scoring method was utilized. The average number of B-lines at T0 was 78±47 with a statistically significant reduction at T1 (44±33, p<.001) and Td (26±26, p<.05). (See Figure 2) Thirty-two patients (73%) were successfully contacted for follow-up.

[figure not shown]
[figure not shown]

Figure 3: Prognostic Value of LUS

Subjects at risk

— B-lines ≤15	60	60	60	60	59	59	59
- - - B-lines >15	40	37	33	31	31	28	27

During the follow-up period (median: 58 days, interquartile range: 44-82 days) 15 events occurred: 2 deaths and 12 all-cause re-hospitalizations. In the subset of patients who experienced events during follow-up, 93% were discharged with persistent presence of pulmonary congestion (> 15 B-lines) as measured by LUS.

Another pilot study of patients (n=100) admitted to a cardiology ward for shortness of breath and clinical concern for AHF demonstrated a statistically significant reduction in B lines at discharge (20+/- 23) vs. admission (48+/-48, p<.0001). At 6-month follow up, patients with ≥ 15 B-lines at discharge were significantly more likely to be re-hospitalized. (HR 11.7 (95% CI 1.3-106.6) (See Figure 3). In 27% of patients with >30 B-lines, no rales were reported by auscultation.

Additional work performed by one our study team members, [name], demonstrated a strong correlation between LUS B-lines and patients undergoing dialysis. This proof of concept supports B-lines as responsive to the removal of fluid. Coiro et.al. recently published a study of LUS performed throughout hospitalization, demonstrating the prognostic significance of residual congestion, as measured by B-lines.

Patients with  $\geq 30$  B lines had significantly worse combined outcome of all-cause mortality and HF re-hospitalizations at 90 days.

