### 4 STUDY DESIGN AND ENDPOINTS

#### 4.1 DESCRIPTION OF THE STUDY DESIGN

A multi-center, prospective, randomized, controlled, unblinded strategy-of-care pilot trial. All potential ED patients will receive an initial LUS scan. Performing LUS is within the standard of care and will be done at no cost to patients. It is not frequently used however, either for diagnosis, prognosis, or to guide clinical therapy. However, treating clinicians will be blinded to these results to minimize contamination of the usual care arm. If clinicians choose to perform their own LUS, those patients will not be excluded. Patients who provide written informed consent and meet all inclusion and no exclusion criteria will be randomized 1:1 to our LUS-guided strategy-of-care vs. usual care. While no further LUS guided intervention will occur for usual care patients, similar to our LUS-guided arm, serial LUS assessments will occur throughout hospitalization as well as pre-specified biomarkers and physical exam. For patients randomized to the strategy-of-care arm, the LUS guided protocol will be initiated and continued until there is a decrease in B-lines to  $\leq 15$  or 6 hours of care has been delivered or patient has left the ED, whichever comes first. Trained research personnel will acquire LUS images. All images will be stored and overread by an independent, expert ultrasonographer blinded to treatment arm.

Safety of patients are paramount. If a potential life threatening etiology is identified, the clinical team will be made aware immediately, irrespective of randomization arm. These occurrences will be recorded in the eCRF. While this will be a rare event, we will a priori establish that an additional patient will be accrued into the study and an additional modified intent to treat population for analysis will be performed, excluding these patients where a life-threatening etiology was identified (i.e. pericardial tamponade).

For patients who do NOT meet eligibility criteria, the results of their LUS will be provided to the clinical team as requested, as these patients are no longer at risk for contamination of the usual care arm.

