#### 4.2.2 EXPLORATORY ENDPOINTS

The following table lists the exploratory endpoints

Table 3: Exploratory Endpoints	
Total DAOOH through 30 and 90 days post-discharge	Association of B-lines at discharge and 30 and 90 day outcomes
Change in biomarkers from presentation to pre-discharge	Association of baseline, discharge, and change with 30 and 90 day outcomes
Time to reach B-lines <15	B lines < 15 at 24 hours and at discharge
Composite of 30-day all-cause mortality, cardiovascular (CV) re-hospitalizations, and CV emergency department (ED) revisits. CV endpoints are defined according to the 2014 ACC/AHA Key Data Elements and Definitions for Cardiovascular Endpoint Events.  Also for same endpoint, but through 90 days	All Cause readmissions, All cause ED re-visits
Change in physical exam findings and body weight from presentation to pre-discharge	Description of ED pharmacologic treatment
Description of hospital based AHF treatment	Inter and intraobserver agreement

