#### Lung Ultrasound (LUS) Protocol

To best determine the potential value of EVLW measurements using LUS, we will assess patients at multiple timepoints throughout hospitalization. (See Figure 1 – Trial design flow below)

Figure 1: Trial Schematic

For diagnostic purposes, previously published protocols have been the most well-studied.

Each LUS scan consists of 8 sectors as seen in figure 2. (Figure reproduced from Volpicelli et.al.7) Trained research personnel will record and count B-lines in each sector as visualized through one respiratory cycle at each of the time points listed in the Figure. At minimum, each stored video clip will be 6 seconds in length. The total number of B-lines for all 8 sectors will comprise the overall score. With training, the entire scan takes less than 10 minutes.

As patient positioning may impact B-lines, patients will be placed at approximately 45 degrees for all scanning. The CRF will be marked if patients are unable to lie at this angle.

- An 8 zone LUS scan will be done at the following times:
  - T00: initial LUS scan (in ED for screening and eligibility)
  - T02: 2-4 hours after initial treatment (in ED) (+/- 30 minutes)
  - T06: 2-4 hours after T02 or pre-ED discharge, whichever comes first (+/- 60 minutes)
  - HD2: 24 hours after initial scan (Day 2) (+/- 6 hours)
  - HD3: 48 hours after initial scan (Day 3) (+/- 8 hours)
  - HD4: Day 4 (anytime during day)
  - HD5: Day 5 (anytime during day)
  - HD6: Day 6 (anytime during day)
  - HD7: Day 7 (anytime during day)
- **If standard care arm do NOT notify the provider of the results**

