## **Training**

All physicians and research staff will undergo in-person training sessions led by the US PI at each site using a standard protocol. Both didactics and proctored bedside scans will occur. This will ensure technique and equipment settings are standardized. Published literature provides strong evidence that LUS can be learned with minimal training: as little as 30 minutes yields excellent correlation with expert sonographers. In addition, established protocols will be utilized for transfer and storage of images.

To ensure ongoing quality assurance, feedback will be provided to each site for every 10 patients, or more frequently as needed if initial review suggests inconsistency. An independent, blinded, expert ultrasonographer will review the images. Concordance with clinical site interpretations will be provided. Additional training will be provided by the

Figure 3: Counting of B-lines using Lung Ultrasound

central reviewer as needed. Inter-rater agreement on B-line counts will be reported at the end of the study.

The CORE lab is led by [name] MD: she is an internationally recognized expert in LUS. She has a proven record of training, both for research and clinical purposes. She has substantial experience in the collation, interpretation, and reporting of LUS images.

**Counting of B-lines:** (Figures courtesy of [name] MD)

B lines will be counted as the number seen per acoustic window. See Figure 3.

In the situation where there is 'white out' or diffuse B lines in a rib space, this will be counted as 10 B-

lines. Half the rib space will be 5. 10 will be the maximum number of B lines per sector.

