### Image Review

All images will be saved as 6-second video clips. Investigators or study staff will label each clip at the time of scan post-enrollment. For example, Scan 0 is at time of enrollment. Scan 24 is 24 hours post-enrollment, Scan 72 is 72 hours post enrollment. All images will also be date/time stamped, which will be recorded in the local site CRF. Investigators or study staff will fill out a table of their count of B-lines, which will be compared to the Core Lab review. If a rib space is completely whited out with B-lines, this will count as 10 B-lines, half the rib space will count as 5. Importantly, the Core Lab will be blinded to the investigator B-line count.

No PHI will be recorded, only a study ID. Each site will separately and securely store linkages from PHI to the study ID per local IRB approved protocols. Currently, all sites have internal processes to store images for quality control as part of their training programs for fellows and residents. Images will then be transferred to a secure, password protected, access limited server with HIPAA grade security.

Local sites will review images to ensure deidentification. Once de-identified, images will be uploaded to a secure, local server with HIPAA grade security. No post-processing will occur. However, prior to upload to the Core Lab, images will be deliberately mixed with other study patients. This is being done to avoid readers from having 'before and after' images. Images will be then uploaded in batches of 5 patients to a secure, HIPAA grade server.

The Core Lab will then download the images. Importantly, the Core Lab will NOT be a study site to minimize any potential bias or failures of de-identification. Furthermore, the Core Lab will not have access to any clinical information on the patient, further limiting the potential for clinical information to bias image interpretation. To minimize the potential bias of having a single sites images reviewed, images from one site will be mixed with other sites upon arrival at the Core Lab. Reviewers will not see images of patients in chronological order or from only one site at a time.

Formal interpretations will be recorded on a standardized, secure CRF accessible only to the Core Lab and the Data Coordinating Center at IU. All investigators will NOT have access to this data until database lock. Applicable back up and secondary storage will occur on a daily basis

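### The exploratory reproducibility model has no term for the individual scan, and intra-observer agreement is promised without any planned repeat read

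*Combined protocol and SAP*

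**What the plan says.** Table 3 in section 4.2.2 lists "Inter and intraobserver agreement" among the exploratory endpoints. The only analysis given for it is one sentence in 10.4.4: "generalized linear mixed-effects models will be fitted to estimate the inter- and intra-observer variability, where both patients and observers are treated as random effects". That sentence does not say which scans enter, whether the unit is a clip, a zone or a total score, or whether any other term is in the model.

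On the data, section 17.3 (Lung Ultrasound Protocol) says "we will assess patients at multiple timepoints throughout hospitalization", and its list and section 7.3.7 give nine time points: T00, T02, T06 and HD2 to HD7. Section 2.2 states that "In AHF patients, B lines generally decrease throughout hospitalization". The sponsor's pilot of 44 patients, scored on 28 sectors, shows the size of the fall: 78±47 in the ED, 44±33 within 24 hours and 26±26 at discharge.

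On the reads, section 4.1 says "All images will be stored and overread by an independent, expert ultrasonographer blinded to treatment arm". Section 17.3 (Image Review) says "Investigators or study staff will fill out a table of their count of B-lines, which will be compared to the Core Lab review", and section 17.3 (Training) says "An independent, blinded, expert ultrasonographer will review the images". The same Training text undertakes to report inter-rater agreement at the end of the study and does not mention intra-rater agreement. Nowhere do the documents describe an observer reading the same scan twice.

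**The concern.** A variance-component model can only separate sources of variation that have a term in the model and replication in the data. Two sources lack one or the other here.

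First, a patient's scans differ because the patient is being decongested. With patient and observer as the only random effects, one patient's scans share a single level, so real differences between them can go only into the residual. If the residual is then reported as intra-observer variability, a treatment response is labelled as reading error.

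Second, intra-observer variability is the spread when one observer re-reads the same images. With one read per observer per scan, the residual mixes that spread with observer-by-scan interaction (reader A counts higher than reader B on some scans and lower on others). No modelling choice can split the two.

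At stake is a reported intra-observer figure that is far too large (if scans are pooled) or wrongly labelled (in either case). This pilot is meant to inform later work with a B-line target, so a misleading figure would be unhelpful, but no confirmatory conclusion depends on it.

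**Working it through.** The plan gives no sample size or precision figure for this analysis, so there is none to reproduce. The check is an expected-mean-square calculation for a Gaussian model.

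**Inputs from the documents.** N = 130 patients. Pilot means 78, 44, 26 and SDs 47, 33, 26 at T = 3 scans. K = 2 reads per scan (site, Core Lab).

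**Assumed inputs.** Within-patient correlation ρ from 0.3 to 0.9. True reading SD of 3 or 5 on the pilot scale, and 1.5 or 2.5 after multiplying the pilot counts by 8/28 as a rough conversion to 8 zones. None of these is in the documents.

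**Step 1: what enters the residual under patient + observer.**

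Residual df = NTK − N − K + 1 = 780 − 130 − 2 + 1 = 649.

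Expected residual variance = (NK/649) × (M + V) + e², with NK/649 = 260/649 = 0.4006 and e the reading SD.

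- M is the fall in the means. The overall mean is 148/3 = 49.33, so M = 28.67² + 5.33² + 23.33² = 1394.7.
- V is individual change around that fall. The variances sum to 2209 + 1089 + 676 = 3974, and twice the SD products is 2 × (1551 + 1222 + 858) = 7262. So V = 3974 − (3974 + 7262ρ)/3 = 2649.3 − 2420.7ρ.

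At ρ = 0.3, V = 1923.1 and the scan part is 0.4006 × 3317.8 = 1329. At ρ = 0.9, V = 470.7 and the scan part is 0.4006 × 1865.4 = 747. On the 8/28 scale both are multiplied by (8/28)² = 0.0816, giving 108.5 and 61.0.

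| Scale | True reading SD | Residual SD, ρ = 0.3 | Residual SD, ρ = 0.9 | Ratio to true SD |
|---|---|---|---|---|
| Pilot, 28 sectors | 5 | √(1329+25) = 36.8 | √(747+25) = 27.8 | 7.4 to 5.6 |
| Pilot, 28 sectors | 3 | √(1329+9) = 36.6 | √(747+9) = 27.5 | 12.2 to 9.2 |
| × 8/28 | 2.5 | √(108.5+6.25) = 10.7 | √(61.0+6.25) = 8.2 | 4.3 to 3.3 |
| × 8/28 | 1.5 | √(108.5+2.25) = 10.5 | √(61.0+2.25) = 8.0 | 7.0 to 5.3 |

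The ratio depends strongly on the assumed reading SD. Section 2.2 cites intra-observer variability as low as 5.1%. Read as an SD, that is 0.051 × 49.33 = 2.5 on the pilot scale, and simulation at ρ = 0.3 to 0.8 then gave residual SDs of 36.5 to 29.2, about 15 to 12 times the input.

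**Step 2: would a fixed time effect be enough?** It removes M but not V, and the df become 647. On the pilot scale with reading SD 5 at ρ = 0.3: √((260/647) × 1923.1 + 25) = 28.2. With reading SD 3 at ρ = 0.9: √((260/647) × 470.7 + 9) = 14.1. It is not enough.

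**Step 3: inter-observer variance.** When both readers cover every analysed scan, change between scans cancels from the observer comparison. It enters only through subtraction of the enlarged residual, which lowers the estimate slightly. With an inter-observer SD of 7.4% of the mean (section 2.2), the true variance is (0.074 × 49.33)² = 13.3. At ρ = 0.5 the scan part is 0.4006 × (1394.7 + 1439.0) = 1135, so the expected estimate is 13.3 − 1135/390 = 10.4. Simulation gave 9 to 12.

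**Step 4: add scan nested in patient.** In simulation the residual fell to 6.30–6.38, against 6.33 put in (2.516²).

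**Step 5: is that residual intra-observer error?** The 6.33 was split three ways between intra-observer error and observer-by-scan interaction: 6.33 + 0, 3.17 + 3.17 and 0 + 6.33. All three gave the same estimate, so the data cannot tell them apart. With one scan per patient, the same holds for observer-by-patient interaction.

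**The case against.** The best defence is that 10.4.4 does not call patients and observers the only terms and does not say that serial scans are pooled. One scan per patient, or separate fits by time point, would be consistent with the sentence, and decongestion would then stay out of the residual. This stands: the inflation is conditional. A reader might infer that the trial will report decongestion as observer error. The documents do not support that, because they leave the unit and the scans unspecified.

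A reader might also infer that all the observer-agreement results are spoiled. They are not. Step 3 shows that the inter-observer variance is not inflated in a balanced layout, and section 17.3 separately compares site and Core Lab counts on the same images, a comparison that decongestion cannot affect.

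The multiple is also open to attack, fairly. The correlation and reading SDs are assumed, the pilot used 28 sectors, the 8/28 conversion is a convenience, and the pilot figures do not reflect this trial's entry rule. The plan names a generalized linear model, and a count model would not report a residual SD in B-lines. The multiple shows direction and rough order, and does not predict what the trial would report.

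A reader might further infer that the definitive trial's endpoint depends on this estimate. Section 3 makes days alive and out of hospital that trial's outcome, and 10.4.4 explores B-line thresholds through ROC methods.

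Finally, that each observer reads a scan once is inferred from the absence of any re-read procedure. The inference is reasonable, but no sentence says so. What the defence does not answer is the promise of an intra-observer estimate with no described data to support it.

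**Conclusion.** The point holds in two parts, and its severity is minor.

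1. Conditional on pooling serial scans under the random effects named in 10.4.4, true within-patient change goes into the residual that would be read as intra-observer variability. The residual SD is then roughly 3 to 12 times the true reading SD under the tabulated assumptions. The inter-observer variance is not inflated, provided that both readers cover the same scans.
2. However the serial scans are handled, the reads described cannot separate intra-observer error from observer-by-scan interaction, so the intra-observer agreement promised in Table 3 and 10.4.4 is not estimable. This rests on there being no same-observer re-reads beyond what the documents describe.

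The analysis is one exploratory item. The primary comparison in 10.4.3, the sample size in 10.5 and the safety analyses do not use it.

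**What to change.** In 10.4.4, state the unit and the scans analysed, and add a random effect for scan nested in patient so that observer differences are estimated within scan. In Table 3 and 10.4.4, delete the intra-observer estimate, or relabel the residual as combined intra-observer and observer-by-scan variability, unless same-observer re-reads are available. These are wording changes that need no new data.

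If the sponsor wants a true intra-observer estimate, some scans must be read again by the same observer without knowledge of the first count. The Core Lab images are already scrambled and mixed across patients, so a sample could be re-inserted, at about 10% more reading if 10% of scans are repeated. That is an added Core Lab procedure needing text in 17.3, so it is optional here.

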## 10.2 STATISTICAL HYPOTHESES

- *Hypothesis 1: LUS guided patients will have less congestion, defined by LUS B-lines <15, than usual care patients at 6 hours after start of treatment. Other measures of congestion, such as serial LUS during hospitalization, physical exam, NTproBNP, and hemoglobin/hematocrit levels will be assessed to determine the superiority or additive value of LUS.*
- *Exploratory Hypothesis: Strategy-of-care patients will have more days alive and out of hospital (DAOOH) at 30 days.*
  - *Strategy-of-care patients will have more days alive and out of hospital (DAOOH) at 90 days.*
- *Hypothesis 2: Each site (n=4) will enroll ~2 patient per month for 18 months.*

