### 10.4.3 ANALYSIS OF THE PRIMARY EFFICACY ENDPOINT(S)

The comparison of binary endpoints (B-lines < 15) will be performed using Chi-square or Fishers exact test, as appropriate.

Potential covariates will also be considered in a logistic regression setting to improve precision, which includes baseline co-morbidities, baseline medications (in particular guideline recommended therapies) in-hospital medications, baseline renal function, serum sodium, natriuretic peptide levels, troponin levels, renal function, baseline blood pressure, and discharge medications. Variables such as physical exam, other vital signs, and hemoconcentration may also be included. For NT-proBNP, a percent change greater than 30% and its association with the primary endpoint will be analyzed. This is based on previous work suggesting a 30% change was a key discriminatory threshold for mortality. For hemoconcentration, any increase in value in both hematocrit and hemoglobin during hospitalization will be considered positive. These covariates are known markers of risk and are standard of care assessments for the vast majority of AHF admissions. Covariates with univariately significant association with the outcome will be included together with the treatment indicator in a logistic regression model. Due to limited sample size, we will limit the number of covariates (including treatment indicator) such that there is 10 events per covariate.

---

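### The models that judge B-lines against other markers for 30/90-day outcomes name no treatment term, so results for post-randomization B-lines may partly reflect the arm

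*Combined protocol and SAP*

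**What the plan says.** Section 10.4.4 first compares B-lines by event status: "We will examine the distribution of B-lines measurements for the groups with and without events separately". ROC curves, accuracy at several thresholds and a possible alternative to 15 B-lines follow. It then sets out five models:

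- Model 1: "First, we include all markers together with B-line measurements in the model (Model 1".
- Model 2: the best-fitting main-effects model from B-lines and the other markers.
- Model 3: "Third, we will explore all main effects models that can be built using only the other markers (Model 3".
- Model 4: a tree, described as a "prediction model using B-lines measurements and the seven other markers". Model 5 is the same without B-lines.

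Models 2 and 3, and Models 4 and 5, are to be compared. The stated product is a score: "These models will allow us to create a discriminating score for the prediction of 30 or 90-day outcomes". Section 10.2 gives the wider purpose of comparing measures of congestion, "to determine the superiority or additive value of LUS". Table 3 in section 4.2.2 lists "Association of B-lines at discharge and 30 and 90 day outcomes", and also baseline values and change. Section 10.4.4 does not say which B-line time point enters the models.

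Elsewhere the plan names arm when it wants it. Section 10.4.3 says: "Covariates with univariately significant association with the outcome will be included together with the treatment indicator in a logistic regression model". The proportional odds model for days alive and out of hospital in section 10.4.4 also compares the arms.

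**The concern.** In the LUS arm, B-lines decide when guided treatment stops (section 4.1) and are the sole guide to further therapy (section 6.1.1). Post-randomization B-lines are therefore expected to differ by arm. If arm is also related to outcome in a way the modelled B-lines do not carry, a model without arm lets B-lines act partly as a proxy for it. The error can go either way. B-lines can look prognostic when they are not, or real prognostic value can be diluted.

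At stake is the judgement on whether B-lines add to NT-proBNP and the other markers, and so whether a later trial should keep targeting them (section 2.2). B-lines are the marker the strategy acts on directly, so the Model 2 v Model 3 comparison is the one most exposed.

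**Working it through.** **Inputs.** From section 10.5: 25% v 50% at the B-line target, 59 per arm, 10% drop-out, 130 in total. From section 4.1: 1:1 allocation. Assumed: an overall event rate of 25%, taken from the 30-day death or re-hospitalization figure in the Protocol Summary, and the effect sizes named below. The plan gives no figure for Models 1 to 5.

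**1. The plan's own figure.** With p̄ = 0.375, power = Φ{[0.25√59 − 1.96√(2 × 0.375 × 0.625)] / √(0.25 × 0.75 + 0.50 × 0.50)} = Φ{(1.920 − 1.342)/0.661} = Φ(0.874) = 0.809. The stated 81% reproduces.

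**2. Link between arm and B-lines at the design rates.**
- Share in the LUS arm among those at target: 0.50/(0.25 + 0.50) = 67%. Among those not at target: 0.50/(0.75 + 0.50) = 40%.
- Phi = 0.25 × 0.5/√(0.375 × 0.625) = 0.26.
- On a normal scale the shift is Φ⁻¹(0.50) − Φ⁻¹(0.25) = 0.67 SD. This is at the end of ED care.

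**3. Binary illustration.** Suppose B-lines have no within-arm value (OR 1) and the strategy has a direct OR of 0.5 on the event. Event risks averaging 25% with that OR are 31.4% (usual care) and 18.6% (LUS).
- Risk if above target: 0.6 × 31.4% + 0.4 × 18.6% = 26.3%.
- Risk if at target: 31.4%/3 + 2 × 18.6%/3 = 22.9%.
- Pooled OR = (0.263/0.737)/(0.229/0.771) = 1.20 instead of 1.

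The same calculation for other values, with no arm-by-B-line interaction:

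| Direct arm OR | Pooled, true OR 1 | Pooled, true OR 2 | Pooled, true OR 3 |
|---|---|---|---|
| 0.33 | 1.34 | 2.58 | 3.81 |
| 0.7 | 1.10 | 2.19 | 3.28 |
| 1 (none) | 1.00 | 2.00 | 3.00 |
| 1.43 | 0.91 | 1.81 | 2.72 |
| 2.0 | 0.84 | 1.65 | 2.46 |

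The row with no direct effect shows no distortion. Moderate direct effects move the OR by about 10%.

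**4. Continuous illustration.** The true log-odds is 0.80 per within-arm SD. The strategy lowers B-lines by δ SD and leaves outcome unchanged, which means a direct arm effect cancels the B-line gain. A hand approximation is 0.80/(1 + δ²/4), because pooling adds δ²/4 to the variance of B-lines but nothing to their covariance with outcome.

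| δ | Hand formula | Logistic fit | Pooled AUC (within-arm 0.70) |
|---|---|---|---|
| 0.67 | 0.72 | 0.71 | 0.69 |
| 1 | 0.64 | 0.62 | 0.68 |

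The fitted losses are about 11% and 22%. They hardly change at event rates of 20%, 25% or 30%. With full mediation (no direct effect) the pooled coefficient is 0.80 at either shift.

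**5. False association, as a gauge only.** This simulation uses 117 patients (130 × 0.9) and B-lines with no within-arm value. With assumed events of 35% v 15%, a 5% test on B-lines rejects about 9% of the time at 0.5 SD and 20% at 1 SD, against about 5% with arm included. At 0.67 SD and 30% v 20% it rejects about 6%.

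**6. Room for an arm term.** 118 × 0.25 = 29.5 events and 130 × 0.25 = 32.5. At 10 events per parameter (the limit section 10.4.3 sets for the primary-endpoint model) about three parameters are supportable.

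**The case against.** The strongest reply is that bias is conditional. Leaving out arm distorts the B-line coefficient only if the strategy reaches outcome other than through the modelled B-lines, or if the association differs by arm. If the strategy works through B-lines, which is the trial's rationale, nothing is lost. This stands. A reader might infer that the prognostic value of B-lines is confounded with the strategy, so that any finding of superiority is unsound whichever way the effects fall. The documents do not support that. Nor do they say outright that the arms are pooled; it is the natural reading of one set of models with no arm term.

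Complete mediation is not established either. Section 10.1 treats the effect of targeting B-lines on outcome as unknown. Section 2.3.1 names kidney injury, over-diuresis, hypotension and possible myocardial injury as risks. Under section 6.1.1, further diuretic differs by arm for patients treated before enrollment, whatever their B-line count.

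Other objections that stand in whole or part:

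- Baseline B-lines precede randomization and cannot differ by arm in expectation.
- The shift at discharge may be below 0.67 SD. Usual care follows the same algorithm unless the clinician declines (section 6.1), guided care ends at 6 hours (section 6.1.2), and inpatient care is unchanged (section 7.1.2).
- The larger figures in step 5 rest on an assumed 35% v 15% split, and section 10.4.4 plans no 5% test on B-lines. No figure has been worked out for the planned reclassification comparisons.
- The stated product is a prediction score, for which omitting arm is mainly a question of transportability. That answers only part of the concern, because section 10.2 also wants a verdict on the value of LUS.

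**Conclusion.** The point holds as a conditional one. Section 10.4.4 names no treatment term for the ROC work or Models 1 to 5, so associations, AUCs and the Model 2 v 3 comparison based on post-randomization B-lines may mix prognostic value with arm. In the illustration with no net effect on outcome, a log-odds of 0.80 reads as about 0.71 at the design-implied shift and 0.62 at 1 SD, while AUC falls by 0.01 to 0.02. Where B-lines have no within-arm value, false association is slight at 30% v 20% events and material only with a large direct effect. There is no bias in the coefficient under full mediation without interaction, and none for baseline B-lines. The effect sizes and the 25% event rate are assumptions. The analyses are exploratory, and the primary endpoint, sample size and safety analyses are unaffected. This is an inexpensive improvement to consider, not a defect that undermines the trial.

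**What to change.** In section 10.4.4, state which B-line time point enters each analysis. For analyses using post-randomization B-lines:

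- Include randomized arm as a fixed term in Models 1 to 3. Keep it in both Model 2 and Model 3, outside the selection step, so that their comparison isolates B-lines.
- Report an arm-stratified AUC (the average of the within-arm values) beside the pooled one.
- Treat by-arm cut-offs and the B-line-by-arm interaction as descriptive only. With about 30 assumed events there are about 15 per arm, too few for a by-arm threshold search or a useful interaction estimate.
- Leave Models 4 and 5 as planned and note the limitation. Offering arm to a tree adjusts nothing unless the tree splits on it.

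The cost is wording and one model parameter out of about three supportable. Arm is already recorded, so no new data are needed. The arm-adjusted coefficient is right both under full mediation and with a direct arm effect, provided there is no interaction.
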